#### **3.1.8** Derivation of durations

#### **3.1.8.1** Time since COPD diagnosis (years)

Time from COPD first diagnosis date to screening will be calculated as (date of first diagnosis of COPD minus date informed consent signed plus one) divided by 365.25. If date of first diagnosis of COPD is partially missing then imputed date will be used (Section 3.1.4.3).

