# Type of Participant and Disease Characteristics:

- 2 Participants who are current or ex-smokers with a tobacco history of ≥ 10 pack-years. Pack-years are calculated as average number of cigarettes per day × number of years / 20. For example, 1 pack-year = 20 cigarettes smoked per day for 1 year or 10 cigarettes per day for 2 years.
- 3 This inclusion criterion has been removed.
- 4 Participants who have a documented history of COPD for at least 1 year. A verbal history of symptoms consistent with COPD from the participant is not sufficient. Acceptable documentation includes
  - Clinic visit (primary or specialist HCP) notes or emergency room/hospital records listing COPD as a current diagnosis
  - Verbal discussion confirming the diagnosis of COPD between the investigator and physician who has access to the participant's medical record. The investigator is required to clearly document this conversation in participant's source document.
- Participants who have a post-BD  $FEV_1/FVC < 0.7$ ) and a post-BD  $FEV_1 > 20\%$  and < 80% predicted normal value at screening. Centralized spirometry will be used for this criteria assessment.
- Participants who have a physician confirmed history of chronic bronchitis as defined as presence of cough and sputum on hos tays for  $\geq 3$  months/year in at least the 2 year period immediately prior to SV1 (see ening). Assessment based on a verbal history consistent with chronic bronclitis is sufficient.
- Participants who have an arrange  $\Im CSS$  score of  $\geq 2$  in cough and  $\geq 2$  in sputum domains assessed over the 14 day preceding SV3.
- Participants who has a documented stable regimen of dual therapy or triple therapy for ≥ 3 months prior to envolment; there should have been no change in treatment after the previous exacerbation prior to entering into the study. Where dual therapy consists of ICS + LABA or LABA + LAMA, and triple therapy consists of ICS + LABA + LAMA. Both dual and triple therapy may be in the form of separate inhalers of fixed dose combination inhalers but may not be in nebulized form. However, all inhalers must be locally approved for the maintenance treatment of COPD. See Section 6.5.1. Acceptable documentation includes:
  - Recent, active medication list as per HCP note
  - Filled prescriptions based on a pharmacy record
  - Another acceptable medical record as per local clinical practice
  - Verbal discussion confirming treatment regimen between investigator and HCPs who

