#### **3.1.8.2** Time since COPD symptoms started (years)

Time from COPD first symptoms date to screening will be calculated as (date of first symptoms of COPD minus date informed consent signed plus one) divided by 365.25. If date of first symptoms of COPD is partially missing then imputed date will be used (Section 3.1.4.3).

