#### **3.1.8.3** Time since last exacerbation (months)

Time since last COPD exacerbation date to screening will be calculated as (date of most recent exacerbation minus date informed consent signed plus one) divided by 365.25 and multiplied by 12.

3.1.8.4	CCI	
CCI		

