#### **3.1.8.8** Time from first IP administration to death (days)

Time from first IP administration to death will be calculated as date of death minus date of first IP administration plus one.

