- Time from first IP administration to onset of AE (days) as derived in Section 3.1.8.6
- Treatment period
- Time from last IP administration to death (days) as derived in Section 3.1.8.8
- Time from first IP administration to death (days) as derived in Section 3.1.8.9
- Received treatment for AE
- Reasonable possibility AE caused by IP

The number of SAEs by SOC and PT term will be summarised by study intervention group. The number and percentages of participants with SAEs by SOC and PT term will be summarised by study intervention group. Key participant information for participants experienced SAEs will be produced using following information:

- Study intervention group
- Participant identifier
- Sex
- Age (years)
- Event term as reported by the investigator
- PT term
- Time from first IP administration to onset of AE (days) as derived in Section 3.1.8.6

- Time from last IP administration prior to AE start date, calculated for AEs starting after the discontinuation of the IP.
- Time from start of IP administration to becoming serious
- Outcome
- Action taken with IP
- Reasonable AE caused by IP

The number and percentages of participants with AEs leading to discontinuation of investigational product by SOC and PT term will be summarised by study intervention group. Key participant information for participants experienced AEs leading to discontinuation of IP will be produced using following information:

- Study intervention group
- Participant identifier
- Sex
- Age
- AE as reported by the investigator
- PT term
- Time from first IP administration to AE onset
- Time from first IP administration to discontinuation of IP
- Seriousness
- Outcome
- Reasonable possibility AE caused by IP

Number and percentage of participants with AE of special interest by maximum reported toxicity grade will be summarised by study intervention group. A list of PT terms for AEs of special interest will be produced. Number of participants with AE for each medical concept (injection site reaction (ISR), serious hypersensitivity, serious infection, progression of heart failure, gastrointestinal adverse reactions, COVID-19) by maximum reported toxicity grade will be summarised by study intervention group.

Number of subjects with COVID-19 related AEs of special interest by SOC and PT will be summarised by treatment group and for total MEDI3506. Similar table will be repeated for the number of subjects with COVID-19 related serious AEs of special interest.

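### The SAP's three COPD history durations subtract in the wrong order and come out negative as written, and the death listing crosses two section references; only descriptive tables are affected

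*SAP*

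**What the plan says.** SAP 3.1.8.1 introduces the interval as running forward to screening ("Time from COPD first diagnosis date to screening will be calculated as") and then gives the formula "date of first diagnosis of COPD minus date informed consent signed plus one) divided by 365.25". SAP 3.1.8.2 uses "date of first symptoms of COPD minus date informed consent signed plus one) divided by 365.25". SAP 3.1.8.3 uses "date of most recent exacerbation minus date informed consent signed plus one) divided by 365.25 and multiplied by 12". SAP 4.2.3.4 lists all three among the COPD characteristics at baseline to be summarised for the ITT population, and Appendix A assigns them to Table 14.1.9.

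For deaths, SAP 3.1.8.8 reads "Time from first IP administration to death will be calculated as date of death minus date of first IP administration plus one", and 3.1.8.9 gives the matching formula from the last dose. SAP 4.2.10.1, in its list of key information for participants who died, has the row "Time from last IP administration to death (days) as derived in Section 3.1.8.8". The next row, for first dose to death, points to 3.1.8.9. Appendix A assigns this output to Table 14.3.3.2, scheduled at all three analyses.

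**The concern.** Each COPD formula takes the earlier date and subtracts the later one, which contradicts the direction stated in the same section. A program written to the letter would fill three rows of the baseline disease table with negative durations.

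In the death listing, each of the two rows sends the programmer to the formula for the other row. Both intervals are plausible positive numbers, so a swap there would be harder to see than a negative disease duration, especially in a table that may have few rows. Time since last dose is one of the facts a reader of a death listing looks for.

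**Working it through.** The plan states no figure to reproduce, so the check applies its formulas to dates.

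**COPD durations.** Let D be the number of days from the event to consent.

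- As written: (-D + 1)/365.25 years, times 12 for months.
- With the dates reversed: (D + 1)/365.25 years, times 12 for months.

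The written form is negative when D is 2 or more, zero when D = 1, and positive only when the event falls on or after the consent date.

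The eligibility criteria in Protocol 5.1 place D well above 2. Criterion 4 reads "Participants who have a documented history of COPD for at least 1 year". Criterion 6 requires cough and sputum on most days for 3 or more "months/year in at least the 2 year period immediately prior to SV1". Criterion 10 requires 1 month free of exacerbation before SV1. Protocol Table 2 schedules consent at SV1.

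| Event before consent | D (days) | As written | Dates reversed |
|---|---|---|---|
| Diagnosis, 1 year | 365 | -364/365.25 = -0.997 years | 366/365.25 = 1.002 years |
| Diagnosis, 10 years | 3652 | -3651/365.25 = -9.996 years | 3653/365.25 = 10.001 years |
| First symptoms, 2 years | 730 | -729/365.25 = -1.996 years | 731/365.25 = 2.001 years |
| Exacerbation, 1 month | 31 | -30 × 12/365.25 = -0.986 months | 32 × 12/365.25 = 1.051 months |
| Exacerbation, 180 days | 180 | -179 × 12/365.25 = -5.88 months | 181 × 12/365.25 = 5.95 months |

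Reading the plus one as attached to the consent date does not help: the numerator becomes -D - 1, still negative. Nor does imputing a partial diagnosis or symptom date under SAP 3.1.4.3, since start dates move to the first of the month or to 1 January, which is earlier still.

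This is not a convention of the section. The other durations readable in 3.1.8 (3.1.8.5 to 3.1.8.9) all subtract the earlier date from the later one.

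**Death intervals.** Take first dose on Day 1, last dose on Day 169 (the scheduled seventh dose) and death on Day 179.

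- 3.1.8.8, from first dose: 179 - 1 + 1 = 179 days.
- 3.1.8.9, from last dose: 179 - 169 + 1 = 11 days.

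| Row in 4.2.10.1 | Section cited | Value if followed literally | Value the label calls for |
|---|---|---|---|
| Last dose to death | 3.1.8.8 (first-dose formula) | 179 | 11 |
| First dose to death | 3.1.8.9 (last-dose formula) | 11 | 179 |

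The two agree only when first and last dose dates are the same, that is, after a single dose.

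**Where the durations are used.** The MMRM, ANCOVA, negative binomial and Cox models (SAP 4.1.2, 4.1.3, 4.1.5, 4.1.6) adjust for the number of exacerbations in the previous 12 months, not for time since the last one. None of the three COPD durations appears among the subgroups readable in SAP 3.1.9.

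**The case against.** The strongest reply is that both slips reveal themselves. The headings and text of 3.1.8.1 to 3.1.8.3 make the intended direction plain, and a column of negative disease durations would be caught at the first dry run. In the death listing the formulas are right, each is headed with the interval it defines, and the row labels are right. A programmer who follows the pointer from the last-dose row lands on a section headed for the first dose. Appendix A specifies Table 14.3.3.2 by template and does not repeat the crossed numbers. Stale numbering occurs elsewhere too: SAP 3.2.4 sends the reader to 3.1.7 for the COPD durations, and 4.2.9 cites 3.1.7.5 for exposure, when both sit in 3.1.8. That looks like clerical drift rather than a fault of design.

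Most of this stands, and it limits the harm. It does not remove the point: a correct program would have to depart from the SAP as written, and the SAP should state the rule that is used.

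A reader might infer more than the documents support:

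- **That the death derivations themselves are wrong.** They are not; only the two section numbers are exchanged.
- **That drug causality would be misjudged.** Under Protocol 8.3.3 and Appendix B 3 the investigator assesses causality case by case. It appears in this listing as a judgement already made, and nothing shows that anyone would form it from the derived interval.
- **That the misplaced plus one matters in itself.** Dropping the minus sign leaves D - 1 days where D + 1 is intended. Two days is about 0.005 years or 0.07 months, which is immaterial beside imputation of partial dates.

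**Conclusion.** The point holds as a correction to the operative SAP text with descriptive consequences only. Programmed as written, the three COPD durations in Table 14.1.9 are negative for essentially every eligible participant, with a size close to the true duration. Programmed as cited, the two death intervals in Table 14.3.3.2 are swapped for any death where first and last dose dates differ.

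The first conclusion assumes that participants meet the inclusion criteria, that recorded or imputed event dates fall before consent, and that COPD symptoms began no later than the 2 years of cough and sputum required at entry. Exceptions are eligibility deviations, a wrong or imputed date on or after consent, and, for the exacerbation interval, consent signed well before SV1.

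It would be a mistake to read this as a threat to the efficacy results or to say that wrong values will be reported. No hypothesis test, model covariate or visible subgroup depends on these durations, and the negative values would very probably be noticed. The swapped death intervals are the likelier of the two to pass unseen.

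**What to change.** Restate SAP 3.1.8.1 and 3.1.8.2 as (date of informed consent minus event date plus one) divided by 365.25, and 3.1.8.3 as the same expression multiplied by 12. In the death list of 4.2.10.1, cite 3.1.8.9 for time from last dose to death and 3.1.8.8 for time from first dose to death. In the same pass, correct the references to 3.1.7 in 3.2.4 and to 3.1.7.5 in 4.2.9, so that both point into 3.1.8. The cost is SAP wording only, plus a check that the programs for Tables 14.1.9 and 14.3.3.2 follow the corrected text. No data collection, model or sample size changes.

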#### **3.1.8.2** Time since COPD symptoms started (years)

Time from COPD first symptoms date to screening will be calculated as (date of first symptoms of COPD minus date informed consent signed plus one) divided by 365.25. If date of first symptoms of COPD is partially missing then imputed date will be used (Section 3.1.4.3).

#### **3.1.8.3** Time since last exacerbation (months)

Time since last COPD exacerbation date to screening will be calculated as (date of most recent exacerbation minus date informed consent signed plus one) divided by 365.25 and multiplied by 12.

3.1.8.4	CCI	
CCI		

#### 3.1.8.5 Duration of exposure (days)

Exposure duration is calculated only for participants in the As-treated population as the total number of days on study drug. Exposure is calculated as the study drug injection last date plus 28 minus study drug injection first date plus one. If any of the first or last dates are missing or partially missing, then imputed dates will not be used, and study drug exposure is set to missing.

#### **3.1.8.6** Time from first IP administration to AE onset (days)

Time from first IP administration to AE onset will be calculated as date of AE onset minus date of first IP administration plus one.

#### **3.1.8.7** Time from last IP administration to AE onset (days)

Time from last IP administration to AE onset will be calculated as date of AE onset minus date of last IP administration plus one.

#### **3.1.8.8** Time from first IP administration to death (days)

Time from first IP administration to death will be calculated as date of death minus date of first IP administration plus one.

#### **3.1.8.9** Time from last IP administration to death (days)

Time from last IP administration to death will be calculated as date of death minus date of last IP administration plus one.

#### 3.1.9 Subgroups

Analysis for the primary efficacy endpoint will be provided for the following subgroups:

- Gender (Male vs. Female)
- Age  $(\geq 40 < 65; \geq 65 80)$
- Race (as collected in CRF)
- BMI in kg/m^2 (<19,  $\geq$ 19 to <25,  $\geq$ 25 to <30,  $\geq$ 30)
- Geographic region (Eastern Europe, Western Europe and North America, Rest of the world. Note: other countries/regions may be added during the course of the study; if new countries are added, and insufficient number of participants from these countries is recruited, then they will be incorporated in the 'Rest of the world' subgroup)
- Baseline FEV1 as percent PNV (<50% vs  $\ge 50\%$ )
- Maintenance medications:
  - ICS vs no ICS (as per stratification)
  - LABA/ICS vs LABA/LAMA/ICS vs LABA/LAMA
- Number of COPD exacerbations in last 12 months as collected in eCRF ( $\leq 1 \text{ vs} \geq 2$ )

CCI
#### CCI

- Smoking status at baseline (current smoker vs former smoker)
- Baseline BCSS based on 14-day average (<median vs ≥median)
- Baseline total SGRQ score (<median vs ≥median)
- Extent of emphysema (< 10% vs  $\ge 10\%$ )
- SARS-CoV-2 using a nucleic acid test (positive at any point vs never positive)
- SARS-CoV-2 using a serology test (negative at baseline and positive at end of study vs negative at baseline and at end of study).

Analysis for the secondary endpoints (change from baseline through Week 28 in pre-BD and post-BD FEV1, pre-BD and post BD FVC) by extent of emphysema (< 10% vs  $\ge 10\%$ ) will be performed.

Modality of the subgroups will only be explored if there is at least 15% of the total participants in this category.

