#### SARS-CoV-2 nucleic acid test

Nasal swab for SARS-CoV-2 nucleic acid test will be performed at SV1, SV2, SV3, SV5-SV14, E/D visit and at any point after for a participant suspected of having COVID-19.

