#### **SARS-CoV-2** serology test

SARS-CoV-2 serology test will be performed at SV3, SV8, SV12 and at Early discontinuation visit.

CCI			
CCI			
3.9.3.1 CCI	CCI		
			E
3.9.3.2 CCI	CCI		
CCI			

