#### **Primary Analysis**

The Primary Analysis will occur once all participants have either completed the Week 12 assessments or withdrawn from the study. The Primary Analysis will include all data captured during 12-week double-blind intervention period, defined as the period between randomization visit (Visit 4) and Week 12 visit (Visit 8). This will include all available data from all visits up to and including Week 12, irrespective of whether the participant discontinued study intervention or received reliever therapy. The statistical analysis will compare of MEDI3506 to Placebo. Personnel from AstraZeneca or its representatives directly associated with the conduct of this study will be unblinded at the Primary Analysis. Personnel from the study sites, and the study participants, will remain blinded until the completion of the Final Analysis.

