- Original data should be display in the listing, the derived values will be displayed with 1 additional decimal place compared to the original data.
- SAS® version 9.3 (as a minimum) will be used for all analyses.

At the time of both, the primary and the end of treatment analyses, all data collected on and prior to data cut-off dates (i.e. respectively Week 12 and Week 28 visit dates for the last subjects) will be cleaned. For the purpose of the statistical analysis, data cut-off rules might be implemented and described in a separate document. All data collected until the time of the final DBL will be included in the final analysis. No cut-off rules will be implemented for the final analysis.

For subjects whose IXRS strata does not match with data collected on the CRF, the IXRS strata will be used in the analyses

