## 4.2.4.4 Subgroup analysis for the primary endpoint

For each of the subgroup factors (see Section 3.1.9) a separate MMRM will be fitted using the same covariates as described for the primary analysis in Section 4.2.4.1. Background medication strata will not be a covariate if background medication strata is the subgroup; geographical region will not be a covariate if it is the subgroup; number of COPD exacerbations in last 12 months will not be a covariate if it is the subgroup. Graphical representations of the LSMeans change from baseline and the two-sided 80% CI over time will be provided for each subgroup by study intervention group using the ITT population. A forest plot (displaying the difference in mean change from baseline in FEV1 at Week 12, together with the two-sided 80% CI and reference line at zero) will be produced for all subgroups.

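### Two SARS-CoV-2 subgroup factors for Week 12 FEV1 are set mostly after randomisation and partly after the outcome, yet are shown unlabelled beside the baseline subgroups

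*SAP*

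**What the plan says.** SAP 3.1.9 lists the subgroups for the primary endpoint, change in clinic pre-bronchodilator FEV1 at Week 12 (SV8). Most are baseline characteristics. Two are not:

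- The swab factor is "SARS-CoV-2 using a nucleic acid test (positive at any point vs never positive".
- The antibody factor, which comes next in the list, is "SARS-CoV-2 using a serology test (negative at baseline and positive at end of study vs negative at baseline and at end of study".

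On testing, SAP 3.8.6 states "Nasal swab for SARS-CoV-2 nucleic acid test will be performed at SV1, SV2, SV3, SV5-SV14, E/D visit", plus tests on suspicion of COVID-19, and "SARS-CoV-2 serology test will be performed at SV3, SV8, SV12 and at Early discontinuation visit". Protocol 5.2, exclusion criterion 1, excludes anyone with a positive nucleic acid test at SV1 or SV2, though mild or asymptomatic cases may be rescreened. Protocol 8.2.6 lets the medical monitor authorise fewer swabs at a site from SV3 onwards.

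SAP 4.2.4.4 fits a separate MMRM for each factor in 3.1.9, and a forest plot "together with the two-sided 80% CI and reference line at zero) will be produced for all subgroups". Appendix A marks the subgroup table (14.2.1.3.3) and the forest plot (Figure 14.2.1.1) for both the Week 12 and the Final analysis. Section 3.1.9 also says that a level is explored only if it holds at least 15% of participants.

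On which data enter the first run, SAP 4 says "The Primary Analysis will include all data captured during 12-week double-blind intervention period". SAP 4.1 refers to cleaning "all data collected on and prior to data cut-off dates (i.e. respectively Week 12 and Week 28 visit dates for the last subjects", and adds that "data cut-off rules might be implemented and described in a separate document". No cut-off applies at the Final Analysis.

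**The concern.** A subgroup contrast is a randomised comparison when membership is fixed before treatment starts. Here it is fixed mostly afterwards. If treatment changes infection or its detection, and infection also relates to FEV1, the arms within a level are no longer comparable. Part of the classification even comes after the outcome: a first positive swab at Week 32 places a participant in the positive level for an FEV1 change measured at Week 12.

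The same Week 12 estimate is also produced twice. The outcome does not change between the runs, but infection status can. A difference between infection levels, or between the two runs, could be read as effect modification when it comes from selection or reclassification. Nothing in the planned outputs tells the reader that these rows differ in kind from those for sex, age or baseline lung function.

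**Working it through.** The plan gives no figure on this point. The design inputs used below (SAP 1.3: 70 per arm, SD 250 mL) are consistent with the plan's sample size: 2 × (1.2816 + 0.8416)² × (250/90)² = 69.6, so 70 per arm.

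**1. Timing of the tests**

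- Swabs after first dose: SV5 to SV14, 10 visits. SV5 to SV8 (Weeks 2 to 12) give 4; SV9 to SV14 (Weeks 16 to 36) give 6. So 6 of 10 follow the outcome, and fewer swabs are taken in total where a reduced schedule is authorised.
- Positives that can predate treatment: only the SV3 swab, or an earlier positive in a rescreened participant.
- Serology: SV3, SV8, SV12 and early discontinuation. The last scheduled sample is at Week 28, and 28 − 12 = 16 weeks after the outcome. The SAP does not say which sample counts as end of study for this factor.
- Both serology levels require a negative baseline, so participants seropositive at baseline fall in neither. Nor do those with no end-of-study result.

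**2. Change of membership between runs**

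The documents give neither infection rates nor enrolment duration. Assumed: N = 140, constant hazard, 30% ever positive by Week 36, and uniform enrolment over E weeks.

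Hazard λ = −ln(0.70)/36 = 0.0099 per week. With the cut-off at the last subject's Week 12 visit, a participant entering at week e has min(36, 12 + E − e) weeks of follow-up. The first-run positive share is the average over e of 1 − exp(−λ × follow-up). The number changing level is 140 × (0.30 − share). The proportion not yet at SV12 is 16/E.

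| E (weeks) | First-run positive | Change swab level | Not yet at SV12 |
|---|---|---|---|
| 26 | 21.7% | 11.7 | 61.5% (86) |
| 52 | 25.8% | 5.8 | 30.8% (43) |
| 78 | 27.2% | 3.9 | 20.5% (29) |
| 104 | 27.9% | 2.9 | 15.4% (22) |

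The last column is before any early-discontinuation samples are counted. At 15% ever positive the changes are 6.2 to 1.5; at 40% they are 14.8 to 3.7.

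If instead status stops at each participant's own Week 12:

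- First-run positive share: 1 − 0.70^(1/3) = 11.2%, or 15.7 of 140. The 15% rule needs 0.15 × 140 = 21, so the positive row is absent at the first run.
- At the Final Analysis it holds 0.30 × 140 = 42 and appears.
- The never-positive row appears at both runs and falls from about 124 to 98, a loss of about 26.

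**3. Possible bias**

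Assumed: a latent infection propensity U, standard normal, correlated ρ with FEV1 change; infection when U exceeds a threshold set by the arm's rate p; the same true treatment effect in everyone. Then E[U | positive] = φ(z)/p and E[U | never positive] = −φ(z)/(1 − p), where z is the 1 − p quantile. The bias is ρ × 250 × the difference between arms. SE = 250 × √(1/n₁ + 1/n₂) with 70 per arm. Range for ρ = 0.1 to 0.3:

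| Infected, by arm | Level | Bias (mL) | SE (mL) | Largest ratio |
|---|---|---|---|---|
| Equal | both | 0 | – | 0 |
| 30% vs 20% | positive | 6.0 to 18.1 | 86.3 | 0.21 |
| 30% vs 20% | never | 3.7 to 11.0 | 48.9 | 0.23 |
| 30% vs 15% | positive | 9.9 to 29.7 | 94.5 | 0.31 |
| 30% vs 15% | never | 5.6 to 16.7 | 48.2 | 0.35 |

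**The case against.** The strongest reply is that little depends on these rows. They are exploratory, carry estimates and 80% intervals with no interaction test, and lie outside the Hochberg family. The 15% rule will often suppress the positive row: it does so at the first run when status stops at each participant's own Week 12, and under every enrolment assumption above when 15% are ever positive by Week 36. Cut-off handling is deferred to a document not available here. With enrolment over 78 to 104 weeks only 3 or 4 participants change swab level. A footnote and Final-only production might be enough.

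Much of this stands. It limits the point to two exploratory rows and makes the change between runs conditional. It does not remove the point. The 15% rule can drop the positive row but leaves the never-positive row, which at 30% ever positive is shown at both runs with different members. Under either reading of the cut-off, end-of-study serology is incomplete at the first run. Labelling and Final-only production are most of the remedy, but a within-level treatment contrast with an interval would still invite a randomised reading.

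A reader might infer that the drug changes infection risk and so biases these rows. The documents do not support that. Protocol 2.3.1 calls serious infection, including SARS-CoV-2, a potential risk, but reports no known direct link with contracting the virus.

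**Conclusion.** The point holds as a matter of analysis choice and should be corrected, though it is not critical. Two of the subgroup factors for Week 12 FEV1 are post-randomisation variables, partly measured after the outcome, and are displayed unlabelled among baseline subgroups at two analyses. Treatment contrasts within their levels are not protected by randomisation.

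Bias is possible but not demonstrated. In the assumed model it is 0 mL at equal infection rates and at most 0.35 SE when one arm has twice the infections of the other. At 30% ever positive, reclassification is about 3 to 12 of 140 with the last-subject cut-off. The loss of about 26 from the never-positive row applies only if status stops at each participant's own Week 12. All these sizes rest on assumed infection rates, enrolment duration and correlation.

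A reader might go further and conclude that the primary result or error control is compromised, or that both infection rows will always appear twice with different members. Neither follows: the primary MMRM does not use infection status, the key secondary family contains no subgroup, and the 15% rule may leave a row shown once or not at all. The baseline-defined subgroups are unaffected.

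**What to change.** Remove both SARS-CoV-2 factors from the efficacy subgroup list in SAP 3.1.9, and so from Table 14.2.1.3.3 and Figure 14.2.1.1. Report Week 12 FEV1 by on-study infection status only as a descriptive summary, labelled post-randomisation and produced at the Final Analysis only, stating which serology sample counts as end of study.

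Optionally, add SV3 serostatus (positive vs negative) as a baseline subgroup under the same 15% rule. It answers a different question, and it may reflect vaccination as well as past infection, since Protocol 4.1.1.1 permits and prefers vaccination more than 30 days before randomisation.

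The cost is SAP wording and changes to a few outputs; no new data are needed. SAP 4.2.10.6 already summarises end-of-study serology in participants seronegative at baseline, so no planned safety output is lost. The small downside is that there would be no inferential FEV1 estimate by on-study infection status.
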